# 3 PROTOCOL SUMMARY

Long title: A randomized controlled adaptive study comparing COVID-19 convalescent plasma (CCP) to non-immune plasma to limit coronavirus-associated complications in hospitalized patients.

Sample Size: n=50

**Study Population:** Hospitalized COVID-19 patients aged ≥18 years with respiratory symptoms and hypoxia, who do not currently require mechanical ventilation, enrolled within 3 days of admission to the hospital OR within 14 days of initial onset of symptoms.

Study Duration: May 25, 2020 to April 30, 2021

**Study Design**: This randomized, pragmatically blinded, placebo-controlled, adaptive trial will assess the efficacy and safety of anti-SARS-CoV-2 convalescent plasma in hospitalized patients with acute respiratory symptoms up to 14 days after the onset of initial symptoms.

A total of 50 eligible subjects will be randomized in a 1:1 ratio to receive either convalescent fresh frozen plasma from blood donors who have recovered from COVID-19 containing antibodies to SARS-CoV-2 or control (standard fresh frozen plasma collected prior to 12/1/2019 or with documented negative SARS-CoV-2 antibody). Should additional anti-COVID agents (anti-viral and/or anti-inflammatory) become available for use as standard of care during implementation, the sample size will be recalculated and increased to account for the estimated impact that these agents may have on the reducing the progression to the primary endpoint of severe hypoxemia.

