To evaluate the clinical efficacy of CCP relative to the control arm in adults hospitalized with COVID-19 according to clinical status (8-point ordinal scale) at Day 29	
 
Death;
 
Hospitalized, on invasive mechanical ventilation or ECMO;
 
Hospitalized, on non-invasive ventilation or high flow oxygen devices;
 
Hospitalized, requiring supplemental oxygen;
 
Hospitalized, not requiring supplemental oxygen - requiring ongoing medical care (COVID-19 related or otherwise);
 
Hospitalized, not requiring supplemental oxygen - no longer requires ongoing medical care;
 
Not hospitalized, limitation on activities and/or requiring home oxygen;
 
Not hospitalized, no limitations on activities.
 

OBJECTIVES	ENDPOINTS (OUTCOME MEASURES)
Additional Secondary Objectives	

 
To evaluate the clinical efficacy of different investigational therapeutics as compared to the control arm as assessed by:
 
Clinical Severity Ordinal scale:
 
Time to an improvement of one category and two categories from Day 0 (baseline) using an ordinal scale.
 
Subject clinical status using ordinal scale at Days 2,5,8,15, 29
 
Mean change in the ordinal scale from Day 1 to Days 2,5,8,15, 29
 
	
 
Clinical outcome assessed using ordinal scale daily while hospitalized and on Days 15, 29 and 120
 
Time to clinical recovery (defined as ordinal score 1-3)
 

 
National Early Warning Score (NEWS):
 
Time to discharge or to a NEWS of ≤ 2 and maintained for 24 hours, whichever occurs first.
 
Change from Day 1 to Days 2,5,8,15, 29
 
	
 
NEWS assessed daily while hospitalized
 

 
Oxygenation:
 
Oxygenation use up to Day 120.
 
Incidence and duration of new oxygen use during the study.
 
Oxygen requirement on day 1,2,5,8,15, 29
 
	
 
Days of supplemental oxygen (if applicable) up to Day 29
 
PaO2/FiO2 ratio or SpO2/FiO2
 
O2 requirement at day 120
 

 
Non-invasive ventilation/high flow oxygen:
 
Non-invasive ventilation/high flow oxygen use up to Day 29.
 
Incidence and duration of new non-invasive ventilation or high flow oxygen use during the study.
 
	
 
Days of non-invasive ventilation/high flow oxygen (if applicable) up to Day 29
 

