
 
Invasive Mechanical Ventilation / extracorporeal membrane oxygenation (ECMO):
 
Ventilator / ECMO use up to Day 29.
 
Incidence and duration of new mechanical ventilation or ECMO use during the study.
 
	
 
Days of invasive mechanical ventilation/ECMO (if applicable) up to Day 29.
 

 
Hospitalization
 
Duration of hospitalization (days).
 
	
 
Days of hospitalization as of Day 29 and day 120
 

Mortality 
 
15-day mortality
 
29-day mortality
 
120-day mortality
 
	
 
Date and cause of death (if applicable)
 

To evaluate the safety of CCP as compared to the control arm as assessed by:	• SAEs

 
Cumulative incidence of SAEs through Day 29.
 
Cumulative incidence of Grade 3 and 4 clinical and/or laboratory AEs through Day 29.
 
Transfusion associated adverse events
 
	
 
Grade 3 and 4 AEs
 
Grade 2 or higher AE's attributed to CCP
 

 
Exploratory Objectives
 
To evaluate the virologic efficacy of CCP
 
	

 
as compared to the control arm as assessed by:
 
Percent of subjects with SARS-CoV-2 detectable in nasal sample at Days 1,5,8,15
 
Quantitative SARS-CoV-2 virus in NP/MTN sample at Days 1,2,5,8,15
 
	
 
Qualitative and quantitative polymerase chain reaction (PCR) for SARS-CoV-2 in NP/MTN swab on Day 1,2,5,8,15 (while hospitalized)
 

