# 4.1.4 **Target population**

This study will enroll hypoxic hospitalized COVID-19 patients, a group that is at elevated risk for poor outcomes and progressive respiratory failure. To date, approximately 30-50% of hospitalized San Francisco COVID-19 patients have required intensive care level treatment, the majority due to respiratory failure[1]. This high progression to ICU level care due to respiratory failure has been seen across the US. This study targets patients who are still early in the course of disease, when CCP may be most effective, the "green zone" described in Figure 2. Once severe respiratory decompensation and ARDS occur and patients have progressed to the "red zone", CCP may be less effective, as was the case with use of CCP in SARS-1 -[8]. The study has been amended to include those on high flow nasal oxygenation, as well as those on nasal cannula. In the ACTT-1 study, 25% of participants on HFNC (ordinal group 6) progressed to mechanical ventilation or death [22] These individuals are at elevated risk of progression to intubation and it is important to understand if CCP can reduce deterioration of respiratory status.

This study will permit enrollment of pregnant women, breastfeeding women and women of childbearing potential. CCP should not pose a pregnancy specific risk, other than the known risks associated with blood product infusions in general. However, for pregnant or breastfeeding women, additional counseling will be provide as to the lack of data for CCP use in COVID-19 infection during pregnancy and lactation and that an adverse event that impacts the participant could also affect an unborn child by affecting maternal health. Pregnant women who chose to enroll will have the pregnancy outcome recorded.

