
 
Oxygenation:
 
Oxygenation use up to Day 90.
 
Incidence and duration of new oxygen use during the study.
 
Oxygen requirement on day 1,2,5,8,15, 29
 
	
 
Days of supplemental oxygen (if applicable) up to Day 29
 
PaO2/FiO2 ratio or SpO2/FiO2
 
O2 requirement at day 120
 

 
Non-invasive ventilation/high flow oxygen:
 
Non-invasive ventilation/high flow oxygen use up to Day 29.
 
Incidence and duration of new non-invasive ventilation or high flow oxygen use during the study.
 
	
 
Days of non-invasive ventilation/high flow oxygen (if applicable) up to Day 29
 

 
Invasive Mechanical Ventilation / extracorporeal membrane oxygenation (ECMO):         
 
Ventilator / ECMO use up to Day 29.
 
Incidence and duration of new mechanical ventilation or ECMO use during the study.
 
 
 
	
 
Days of invasive mechanical ventilation/ECMO (if applicable) up to Day 29.
 

 
Hospitalization
 
Duration of hospitalization (days).
 
	
 
Days of hospitalization as of Day 29 and day 120
 

Mortality 
 
15-day mortality
 
29-day mortality
 
120-day mortality
 
	
 
Date and cause of death (if applicable)
 

To evaluate the safety of CCP as compared to the control arm as assessed by:	• SAEs

 
Cumulative incidence of SAEs through Day 29.
 
Cumulative incidence of Grade 3 and 4 clinical and/or laboratory AEs through Day 29.
 
Transfusion associated adverse events
 
	
 
Grade 3 and 4 AEs
 
Grade 2 or higher AE's attributed to CCP
 

 
Exploratory Objectives         
 
To evaluate the virologic efficacy of CCP as compared to the control arm as assessed by:
 
 
 
Percent of subjects with SARS-CoV-2 detectable in NP/MTN sample at Days 1,5,8,15
 
Quantitative SARS-CoV-2 virus in NP/MTN sample at Days 1,2, 5,8,15
 
	
 
Qualitative and quantitative polymerase chain reaction (PCR) for SARS-CoV-2 in NP/MTN swab on Day 1,2,5,8,15 (while hospitalized)
 

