# 6.2 Statistical Analysis

# 6.2.1 **Primary endpoint**

Our primary hypothesis is that by providing anti-SARS-CoV-2 plasma, the rate of progression to mechanical ventilation or death will be decreased as compared to the rate in in the group receiving control plasma. We will apply a Fisher exact test to compare the combined endpoint of mechanical ventilation/death respiratory failure rates between the two groups occurring by day 15. 29. All analyses

will be conducted with a modified intention-to-treat approach, which excludes randomized subjects who do not initiate an infusion of the study plasma. As secondary analysis, we will also analyze the reduced oxygenation rate, requirement for supplemental oxygen rate, length of hospitalization, time to recovery (ordinal score 1-3) and mechanical ventilation rate, respectively, as well as occurrence of the primary endpoint by day 29 Statistical inference will be based on a two-sided Type 1 error rate of 0.05 and 95% confidence intervals.

Participants who are intubated for reasons other than hypercarbia/hypoxia, such as for a procedure or airway obstruction, will have ventilation settings evaluated to determine if need for ventilation due to hypoxia is meet. This will be determined by >12 hours of requirement for a mandatory mode of ventilation (volume control or pressure control) or Fi02 of > 40%. External adjudication of intubation for non-hypoxic/hypercarbic indication will be conducted.

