# 6.2.3 Other secondary endpoints:

Differences in time-to-event endpoints (e.g., death, hospital discharge) will be summarized by treatment arm using Kaplan-Meier curves and 95% confidence bounds. Duration of events (e.g., days of hospitalization, supplemental oxygen, ventilation) will be summarized by treatment arm by median days with quartiles. Binary data (e.g., incidence of new oxygen use) will be summarized by treatment arm as percentages with 95% confidence intervals. Categorical data (e.g., 29-day mortality, ordinal scale by day) will be summarized by treatment arm as proportions by category and using odds ratios with 95% confidence intervals.

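### Days on invasive ventilation/ECMO have no stated value for patients never ventilated, so the planned median is either confined to users selected after randomisation or almost surely 0 in both arms.

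*Combined protocol and SAP*

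**What the plan says.** The endpoint tables in section 3 (Protocol Summary) and section 5.1 list, among the additional secondary efficacy comparisons with control, "Days of invasive mechanical ventilation/ECMO (if applicable) up to Day 29" and "Days of non-invasive ventilation/high flow oxygen (if applicable) up to Day 29". The ventilation objective beside the first is "Incidence and duration of new mechanical ventilation or ECMO use during the study".

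The analysis rule is in section 6.2.3: "Duration of events (e.g., days of hospitalization, supplemental oxygen, ventilation) will be summarized by treatment arm by median days with quartiles". No test is named for durations. Incidence is handled separately: "Binary data (e.g., incidence of new oxygen use) will be summarized by treatment arm as percentages with 95% confidence intervals". Section 6.2.1 also lists "time to recovery (ordinal score 1-3) and mechanical ventilation rate" among the secondary analyses, and states that all analyses are modified intention-to-treat (mITT), leaving out only randomised patients who never start the infusion.

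Two facts about entry matter. Section 3 restricts the trial to patients "who do not currently require mechanical ventilation". Section 4.1.4 says: "The study has been amended to include those on high flow nasal oxygenation, as well as those on nasal cannula".

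Nowhere do the documents say whether a patient who never receives a given support scores 0 days or is left out, how a death before Day 29 is scored, or whether high-flow days already running at entry count towards new use.

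**The concern.** The plan leaves open which patients enter the median, and for invasive ventilation/ECMO both readings fail.

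- **Users only.** The if-applicable qualifier and the phrase about duration of new use allow this reading. Every ventilation course starts after randomisation, and preventing ventilation is part of the primary hypothesis. The users in each arm are therefore selected by the treatment effect, and their durations are no longer a randomised comparison. If plasma prevents the shorter courses, the remaining users have longer ones and a benefit looks like harm.
- **All patients, never-users at 0.** Randomisation is respected, but with well under half of each arm ventilated the median is 0 in both arms for almost any effect.

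The choice would be made with data in hand. Section 4.1.9 also plans to pool the data with other plasma trials, so an undefined variable could carry over into that work.

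**Working it through.** **Inputs.** Section 6.1 gives 50 patients randomised 1:1, so 25 per arm; I take all 25 as mITT. It assumes 32% control progression to ventilation or death. It also cites 20% and 34% on standard of care, and 8% and 25% on remdesivir, for patients on supplemental oxygen and on high flow/non-invasive ventilation respectively. The documents give no ever-ventilated rate to Day 29, so I show 8% to 40%.

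**The plan's own figure.** No figure is given for durations. The nearest is the Fisher rejection table in section 6.1. Its row of 8/25 v at most 1/25, the only one used here, reproduces: two-sided p = 0.0232 at 8 v 1.

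**Users-only reading.** If the events in that row are taken as ventilations, a significant trial would set about 8 control durations against at most 1 active duration. At an 8% active rate, P(X ≤ 2) for X ~ Binomial(25, 0.08) is 0.677, so two or fewer users is the likely outcome.

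An assumed example shows the direction problem. Control has 8 of 25 ventilated, four for 5 days and four for 15. Plasma prevents the four short courses.

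- Users' median: 10 days (control) v 15 days (plasma).
- Mean over all 25: (4×5 + 4×15)/25 = 3.2 v (4×15)/25 = 2.4 days.
- All-patient median: 0 v 0.
- All-patient upper quartile (19th ordered value): control has 17 zeros, so it is 5; plasma has 21 zeros, so it is 0.

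**All-patients reading.** With n = 25 the median is 0 when at most 12 patients are users, and the upper quartile is 0 when at most 6 are.

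| Ever ventilated | P(X ≤ 12): median 0 | P(X ≤ 6): upper quartile 0 |
|---|---|---|
| 8% | 1.000 | 0.997 |
| 20% | 0.9996 | 0.780 |
| 25% | 0.997 | 0.561 |
| 32% | 0.970 | 0.266 |
| 34% | 0.952 | 0.201 |
| 40% | 0.846 | 0.074 |

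Multiplying the arms, P(both medians 0) is 0.97 at 32% v 4%, 0.97 at 32% v 16%, 0.95 at 34% v 25%, and 0.970 × 0.970 = 0.94 at 32% in both. The upper quartile in an arm is non-zero with probability 1 − 0.266 = 0.73 at 32% and 1 − 0.780 = 0.22 at 20%.

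**Non-invasive ventilation/high flow.** The same formula depends on the share who ever use it. P(both medians 0) is 0.965 at 30%, 0.72 at 40%, 0.25 at 50%, 0.02 at 60%, and below 0.001 at 70% or more. The documents do not give the share on high flow at entry. If the 32% is read as a mixture of the 20% and 34% groups, the implied share is (32 − 20)/(34 − 20) = 86%, and the medians would then almost surely be above 0 if baseline days count. That is only an inference, and the eligibility item in section 5.4 excluding patients already in the ICU could lower the share.

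**The case against.** The strongest reply is that the plan already contains the remedy. Section 6.2.1 puts all analyses on the mITT population. The if-applicable phrase is also attached to date and cause of death, which suggests a note about data recording and not an analysis set. Quartiles accompany the median, and in the example above they read 0 (0 to 5) v 0 (0 to 0), which shows the difference. Incidence is reported beside duration, so a reader would see 8/25 v 4/25 next to any users-only medians. The reversal also needs plasma to prevent short courses; preventing long ones would shorten the users' median.

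Much of this stands. A reader might infer that the planned summary cannot show any difference whatever plasma does. The quartiles rule that out for ventilation. A reader might extend the 0 v 0 result to high flow, but patients already on high flow are eligible and their share is unknown. A reader might also take the 20% and 0% on ventilation in the ordinal table of section 6.1 as ever-ventilated rates. They are status categories in a detectable-difference scenario. They leave out patients already extubated or who died after ventilation.

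What does not stand is that the gap is closed. The mITT sentence defines the population, not the value a never-user contributes. The quartiles help only if that value is 0, and at a 20% rate the upper quartile is still 0 with probability 0.78. Incidence says how many were ventilated, not for how long.

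**Conclusion.** The concern holds for invasive ventilation/ECMO. With no value for never-users, the stated method gives either a comparison selected on a post-randomisation event (about 8 v at most 1 patient at the plan's rejection boundary) or a median that is 0 in both arms with probability about 0.94 to 0.97 at a 32% control rate. The upper quartile retains partial information.

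For non-invasive ventilation/high flow the supported point is narrower: the never-user value is missing, and it is unclear whether days on baseline high flow count as new use.

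The figures assume 25 mITT patients per arm. They use 32% as a stand-in for ever-ventilated by Day 29. That rate includes deaths without ventilation and rests on 15-day data, so the true rate could lie on either side. The direction reversal is an illustration with assumed courses, not a prediction.

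This is a secondary outcome that the plan only describes, in a 50-patient trial. The primary analysis is untouched, and the change is a cheap improvement.

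**What to change.** In section 6.2.3 and both endpoint tables:

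1. Drop the if-applicable qualifier. Define each duration in every mITT patient, with 0 days for those who never received the support.
2. State whether days on high flow already running at entry count.
3. Compare arms over all mITT patients with a summary that does not collapse and has a stated death rule. One option is support-free days to Day 29, with death as the worst value, compared by a rank-sum test allowing for ties. Its median should not be the headline, because never-ventilated survivors would all share the maximum and the same collapse would recur there.
4. Show mean days per patient with a bootstrap 95% CI alongside. It should not stand alone, because without a death rule an early death on ventilation counts as few days and looks favourable.
5. Report days among users as description only.

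The cost is plan wording and no new data. The downsides are that the mean is sensitive to a few long courses and that precision is low with 25 per arm, especially if one arm has only one or two users.

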# Study population

#### Inclusion Criteria for Enrollment:

- 1. Patients ≥18 years of age
- 2. Hospitalized with COVID-19
- 3. Enrolled within 72 hours of hospitalization OR within day 14 from first symptoms of illness
- 4. Pulmonary infiltrates on chest imaging
- 5. Oxygenation of <95% on room air
- 6. Laboratory confirmed COVID-19

#### **Exclusion Criteria**

- 1. Contraindication to transfusion due to inability to tolerate additional fluid, such as due to decompensated congestive heart failure
- 2. Baseline requirement for oxygen supplementation prior to COVID-19 infection or use of positive pressure therapy for sleep disordered breathing
- 3. Currently experiencing severe hypoxemic failure, as defined in study endpoints
- 4. Prior receipt of plasma products, IVIG, or hyperimmune globulin within past 3 months
- 5. Not currently enrolled another interventional clinical trial of COVID-19 treatment.

Note: If taking medications with potential anti-COVID activity for the purpose of COVID-19 treatment that do not yet have data to support efficacy, such as IL-6 antagonists these medications must be stopped prior to enrollment. Receipt of current standard of care COVID-19 treatment, including remdesivir and dexmethasone is permitted and should be recorded as concomitant medications.

# 4 RATIONALE/BACKGROUND:

### 4.1 Background and scientific rationale

Human convalescent plasma is a treatment option for COVID-19 and could be rapidly available when there are enough people who have recovered and donate plasma containing high titer (anti- SARS-CoV-2) neutralizing immunoglobulins. As more individuals contract COVID-19 and recover, the number of potential donors will continue to increase, to allow greater use.

Use of convalescent plasma is a form of passive antibody therapy that involves the administration of antibodies to a given agent to a susceptible individual for the purpose of preventing or treating the infectious disease it causes. In contrast, active vaccination requires the induction of an immune response that takes time to develop and varies in efficacy depending on the vaccine recipient. Some immunocompromised patients fail to achieve an adequate immune response to active vaccination and at present, there are no vaccines to prevent COVID-19. When given to a susceptible person, antibody used for therapy will circulate in the blood, reach tissues and hopefully mediate a beneficial effect by antimicrobial and anti-inflammatory activity [2]. Depending on antibody amount and composition, protection conferred by transferred immunoglobulin can last from weeks to months.

Passive antibody administration is the only means of providing immediate immunity to susceptible persons and immunity of any measurable kind for susceptible, including immunocompromised patients with Covid-19. This kind of antibody therapy has a storied history going back to the 1890s and was the only means of treating certain infectious diseases prior to the development of antimicrobial therapy in the 1940s [3, 4]. Experience from prior outbreaks with other coronaviruses, such as SARS-CoV-1 shows that such convalescent plasma contains neutralizing antibodies to the relevant virus [5]. In the case of SARS-CoV-2, the anticipated mechanism of action by which passive antibody therapy would mediate protection is viral neutralization. However, other mechanisms may be possible, such as antibody dependent cellular cytotoxicity and/or phagocytosis. Convalescent serum was also used in the 2013 African Ebola epidemic. A small non-randomized study in Sierra Leone revealed a significant increase in survival for those treated with convalescent whole blood relative to those who received standard treatment [6].

When used for therapy, antibody is most effective when administered shortly after the onset of symptoms. The reason for temporal variation in efficacy is not well understood but could reflect that passive antibody works by neutralizing the initial inoculum, which is likely to be much smaller than that of established disease. Another explanation is that antibody works by modifying the inflammatory response, which is also easier during the initial immune response, which may be asymptomatic [7]. For example, passive antibody therapy for pneumococcal pneumonia was most effective when administered shortly after the onset of symptoms and there was no benefit if antibody administration was delayed past the third day of disease [3]. Clinical outcomes after convalescent antibody therapy were better when it was administered to ill patients SARS-CoV-1 within 14 days after onset of symptoms (discussed below) [8]. Our goal is to treat patients who are sick enough to warrant hospitalization but do not have severe respiratory disease and/or ARDS.

